The manual describes in detail processes which aim to improve end of life care for people with severe memory problems by:

- Enabling holistic individualised person centred care.

- Providing an interdisciplinary care leader (ICL) who will act as a central resource for health care professionals, care home staff and family carers involved in the care of people with severe memory problems.
- Developing links and joint working between all those involved in the care and management of people with severe memory problems to establish a model of integrated care.
- Improving the understanding of what is meant by an individualised personal care plan and how such a plan might be worked out and used in practice
- Providing support to front-line staff and managers in care homes to enable them to hold uncertainty and manage risk in people with severe memory problems to avoid unnecessary place of care transfers.
- Identifying, facilitating and supporting the training needs of care home staff in the care of those with severe memory problems.
- Recognising the needs of family carers, including being alert to possible anxiety and depression.
- Supporting the commissioning of effective and sustainable systems to deliver these objectives.

Overview of the intervention

The enhanced model of care delivered by the intervention will run for 6 months. For a detailed description of the intervention see Appendix 1. Facilitating effective clinical change in complex health and social care systems can be challenging. Compassion aims to set out a clear pathway of the actions that need to be taken, and by whom, for its effective implementation. This includes integrating change within existing systems to underpin current expertise and developing an understanding of what is needed for continued best practice. The key people involved in delivering Compassion for the pilot phase are listed below.

Interdisciplinary Care Leader (ICL)

The ICL will be a new post funded through the Compassion research project. The main responsibilities of the ICL will include:

- Developing an understanding of the health and social care professionals, pathways and services relevant to the care home residents with severe memory problems that are currently available.
- Working with the care home staff to identify and assess residents suitable for inclusion in the intervention.
- Establishing who the members of the core team involved in care will be, co-ordinating the weekly meetings and working within the core team to develop and implement personalised care plans for each resident included in the intervention.

- Establishing the wider clinical team, co-ordinating monthly meetings and maintaining effective communication to facilitate integrated co-ordination of care and the development of good working relationships between all health and social care professionals involved in the care of those with severe memory problems.
- Working with the care home staff to identify and support their educational and training needs, including fostering a culture of respect, dignity and quality of care for all residents and their family carers supporting someone with severe memory problems.
- Meeting with and supporting family carers to ensure their needs and wishes are understood.
- Collecting process data to support evaluation of the intervention.

The ICL will receive training in standard procedures with regard to clinical and information governance, safeguarding of vulnerable adults and the Mental Capacity Act prior to commencing in post. He/she will keep an anonymised reflective diary and will be supported by the research team at the Marie Curie Palliative Care Research Unit.

The Core Team

The core team comprises a range of existing staff who already regularly visit the homes and are responsible for overseeing the medical, nursing and social care needs of residents. During the intervention they will work with the ICL and are the key personnel required to deliver Compassion. The team will meet weekly and includes:

[figure not shown]
- Clinical Lead Professional (GP supporting the care home, Geriatrician or Old Age Psychiatrist)
- Member of care home staff (care home manager or floor/ unit manager)
- Interdisciplinary Care Leader

The Wider Team

The wider team includes local health and social care professionals and specialist services involved in the care of people with severe memory problems. The team includes staff from General Practice, Care of the Elderly, Old Age Psychiatrist, Palliative Care, Social Services and Community services such as District Nursing, Social Workers, Speech and Language Therapy, Dietetics, Tissue Viability, Physiotherapy and Occupational Therapy. However, the exact composition will depend on local working practices and the availability of key personnel. The wider care team will meet monthly with the core team; meetings may be face to face or via links such as conference calling. The organisation, communication, facilitation and recording of meetings will be the responsibility of the ICL but the team will be required to appoint a lead to chair the meetings.

The Compassion flow chart, shown below, outlines the steps of the intervention pathway, the roles and the responsibilities of those participating, and the work required within each step of the pathway.

Compassion Intervention flow chart for pilot study

Education and Training considerations

Current education and training provision on end of life care in for people with severe memory problems within the CCG area will be scoped and mapped.

The ICL will work with the care home to help to establish and address the training and educational needs of their staff. This will be primarily by working alongside the staff but may also include one to one reflective discussions with key staff members. Learning and training needs will be addressed in a variety of ways but will include shared working and mentoring, use of online learning resources and formal topic based teaching sessions from local services

and experts if required. Training will be feasible within timing, staffing and financial constraints and will be agreed with the care home manager.

Education and training provided as part of the intervention will aim to enable care staff to recognise and respond effectively to the needs of people with severe memory problems and to support family carers with increased confidence and competence. Education and training will link to the core competencies outlined in the document “Developing end of life care practice: A guide to workforce development to support social care and health workers to apply the common core principles and competences for end of life care” (Skills for Care, Skills for Health, National End of Life Care Programme. 2012) and will include, communication skills, with residents suffering from severe memory problems and their family carers, assessment and care planning, advance care planning, symptom management to maintain comfort and wellbeing, knowledge and values.

DATA COLLECTION

Our enhanced care model may have an impact at a number of levels, for example on the individual resident and their family carer, on care home staff, at processes which occur at the level of care home management and on the intervention team itself. This is a feasibility study and thus we have to collect data on a range of outcome and process measures, to detect any impacts which the intervention may have on a complex care system and those who reside and work within it. Our measures map onto our key objectives which are to understand the barriers and facilitators to the implementation of the enhanced care model, to assess feasibility and acceptability of the model and to understand the impact of this model on individual residents and their family carers. Data collection is summarised in table 3 (below).

Process data: these will be collected by the ICL and the team delivering the enhanced service. It is evaluation data much of which is already routinely collected within this setting and is required for national NHS and social care end of life care targets and key commissioning performance indicators (marked with * in outcomes table). The data will give us information on the feasibility and acceptability of the intervention and barriers and facilitators to its implementation. This data will be anonymous at source and not collected at an individual level.

Data on individual outcomes: these data will be collected by the research team who will work independently of the enhanced service implementation team. We will collect data from residents with severe memory problems who receive the service, their family carers, individual care home staff and individual members of the intervention team. Thus to collect these data will require individual informed consent (or in the case of care home residents who may lack capacity, assent). For further information in our consent processes please see page 8.

Table 3: Process and outcomes measures

	Process data	Information on individual outcomes and perspectives
Enhanced care team	
 • Number of residents reviewed • Contacts with family carers • Attendance at team meetings • Number of individual care plans made* • Referral to other specialists 	
 • Experience of participating in the enhanced care intervention • Experience of participating in the enhanced care intervention • ICL reflective practice diary • Barriers and facilitators to the enhanced care intervention
Care home level data	
 • Use of pain tools * • Number of residents with pain management plans* • Recording of surrogate decision makers* • Number of residents with resuscitation status recorded* • Number of deaths within the care home in the last month* • Recording of preferred place of death* • Number of deaths in the usual/preferred place of care* • Numbers of ambulance transfers to acute care* • Visits by out of hours primary care* 	
Care home staff	
 • Education and training needs of care home staff and how these were addressed 	
 • Experience of participating in the enhanced care intervention
Family carer	
 • Numbers who have a needs assessment 	
 • Satisfaction with the intervention • Burden • Anxiety and depression • Satisfaction with general care • Quality of life 
If the resident dies:
 
 • Satisfaction/quality of end of life care
Care home resident	
 • Number of baseline assessments • Number of review assessments 	
 • Severity of impairment • Pressure sores risk and severity • Pain • Agitation • Behavioural Symptoms • Symptom management at end of

		
life
 
 • Quality of life • Resource Utilisation • Number of hospital admissions • Sentinel events • Use of parenteral feeding • Use of personalised care plans • Death in usual /preferred place of care 
If the resident dies:
 
 • Use of medication • Burdensome interventions • Adherence to individual care plan
--	--	---

*evaluation data which is already routinely collected within this setting and is required for national NHS and social care end of life care targets and key commissioning performance indicators

Enhanced care team process data

The ICL will record process data on a pro-forma to enable monitoring and evaluation of the enhanced service. These data will be collected on a monthly basis, it will be anonymised and not identifiable at the level of individual residents. These data give us information on the feasibility and acceptability of the intervention and will include:

- Number of residents reviewed by the enhanced care team
- Number of contacts with family carers (by phone and face to face)
- Attendance at team meetings
- Number of individual care plans made by the enhanced care team
- Referral to other specialists outside the care home, for example dietician, speech and language therapists, tissue viability nurses
- Education and training needs of care home staff and how these were addressed i.e., by individual training sessions, referral to online training resources

In addition the ICL will keep a reflective diary (carefully written to ensure anonymisation and confidentiality) recording their experiences of scoping for and implementing the intervention, including notes on care home dynamics, their interactions with the core and wider teams, the care being delivered by staff and any changes being observed that may not be captured by the outcome measures.

Care home level process data

This data will be collected on a monthly basis by the care home manager (to comply with the UK Data Protection Act 1998) in collaboration with the ICL. It will be anonymised and not identifiable at the level of individual residents. Much of this data should already be routinely

collected and is required by governance organisations and local health and social care commissioners in their assessment of whether services are meeting statutory key performance indicators. The ICL will document:

- Whether pain tools are being routinely used in the care home
- The number of residents with pain management plans
- The recording of surrogate decision makers in the care home records
- Number of residents with resuscitation status recorded
- Number of deaths within the care home in the last month
- Recording of preferred place of death
- Number of deaths in the usual/preferred place of care
- Numbers of ambulance transfers to acute care
- Visits by out of hours primary care

Acceptability of the intervention to care home and enhanced care team staff

We will explore the experience of participating in the intervention with members of the enhanced care team and care home staff. We will conduct qualitative interviews with a purposively sampled selection of staff at the end of the project. These interviews will occur at the end of the intervention period. We will explore the staff experience of the enhanced care team using a structured topic guide which maps onto key areas of current UK end of life and social care policy, for example, how they found working with the ICL, whether the ICL enhanced the way they performed their role, whether the enhanced care model changed how they recognised symptoms such as pain and how these were managed (for interview guide see Appendix 2). Interviews will be audio taped and transcribed verbatim (anonymised). They will last no longer than one hour and participants will be offered the opportunity to review transcripts to ensure accuracy.

Outcomes for care home residents receiving the intervention

These data will be collected independently by the research team only on those residents who have given informed consent to participate or whose relatives have given signed assent for their participation

Demographic information (age, marital status, previous employment) will be collected at the beginning of the evaluation. Severity of dementia will be measured using the FAST scale. At study entry information from GP notes will be obtained by the research team, including: medical co-morbidity (the Charlson Co-morbidity Index (CCI): which includes 19 diseases weighted on the basis of their association with mortality). This allows for the documentation of painful co-morbidities (29). We will document medications from GP prescriptions (e.g. antibiotics, analgesia and antipsychotics). We will document the presence of advance directives, care plans and specific requests regarding hospitalization and resuscitation.

Clinical assessment

Researchers will assess participants and document their symptom burden with the proforma used in our cohort study (25). It consists of a typical, detailed generalist approach to palliative care.

Functional Assessment Staging Scale (FAST): This observational scale describes a continuum of seven successive stages of functional impairment, from normality to the most severe dementia (5). (See Table 2; *Recruitment of people with severe memory problems for evaluation of outcomes*)

Bedford Alzheimer Nursing Scale (BANS): This brief 8-item scale is used to stage the level of severe memory impairment in terms of factors such as eye-contact and speech (30). (See Appendix 2).

Pressure sores risk and severity: The Waterlow Scale will be used for the assessment of risk for developing pressure sores (See Appendix 3). It has high inter-rater reliability and sensitivity (31). The Stirling Scale measures the extent of damage from a scale of 1, Non-blanching erythema of intact skin to 4, full-thickness wound, which involving subcutaneous tissue and the deep fascia (32). (See Appendix 4).

Observational scales completed with care home staff or family carers

Pain Assessment in Advanced Dementia (PAINAD): This measures pain during care tasks and at rest. A comprehensive systematic review has identified this tool as having sensitivity and clinical utility (33). (See Appendix 5).

Cohen Mansfield Agitation Inventory (CMAI): This observational scale rates a range of behaviours many of which are relevant and challenging in dementia, for example wandering, grabbing on to people and pushing. It enables measurements over short timescales and is completed with a carer or staff member (34). (See Appendix 6).

The Neuropsychiatric Inventory (NPI): is a brief caregiver questionnaire that is used to assess behavioural and psychological symptoms commonly observed in residents with severe memory problems (BPSD) i.e. psychosis, mood disturbances, agitation, personality changes, pacing, wandering, and appetite disturbances. Its use in primary care is recommended, as it not only assesses the severity of the symptom for the patient but also the distress that the symptom causes the caregiver (35). (See Appendix 7).

Symptom Management at the End of Life in Dementia Scale (SM-EOLD): Is a tool used to assess comfort and pain during the prior 30 days (36). (See Appendix 8).

The Quality of Life in Late Stage Dementia Scale (QUALID): is a validated scale that assesses quality of life over the prior week (37). (See Appendix 9).

Resource Utilisation in Dementia (RUD)-lite: Resource Utilisation in Dementia (RUD)-lite: Is a short version of the RUD structured interview to assess costs of care including patient accommodation, informal care, community care and hospitalizations (38). (See Appendix 10).

Monthly follow up assessments

Participating residents will be reviewed every four weeks in the care home by the research team, for a maximum of six months, or until death. We will repeat measures: the generalist clinical assessment; Waterlow, Sterling, CMAI, NPI, BANS, PAINAD, SM-EOLD, QUALID, and the RUD-lite. We shall also record prospectively the number of acute hospital admissions, the reasons for these, “burdensome interventions” e.g. enteral feeding tubes (27) and “sentinel events”, defined as “new medical conditions that have the potential to lead to a significant change in health status and a shift in the goals of care” e.g. pneumonia, hip fracture (6). Prescription medications and use will also be collected.

Data collection post death

The Comfort Assessment in Dying with Dementia Scale (CAD-EOLD) (36) (See Appendix 11) will be completed with care home staff within 14 days of the resident’s death to assess their level of comfort and pain in the seven days prior to their death. Through a review of care home notes we shall record use of medication at the end of life (i.e. “just in case” prescribing, opiates, syringe drivers and artificial hydration or nutrition), sentinel events and burdensome interventions. We will examine adherence to any individual care plans which were made.

Outcomes for family carers

Data will be collected independently by the research team during face to face interviews at study entry within 14 days of the initial resident assessment and then every month, by post or over the telephone (family carers’ preference). If family carers are un-contactable for more than 2 months or withdraw from the study we will document the reason and aim to continue to include the person with severe memory problems in the study, unless the carer specifically withdraws their assent.

At project start

We will collect demographic data to include age, sex, ethnicity, education, employment and occupation (present or previous), marital status, relationship to the care home resident, the number of years spent caring and any other caring responsibilities e.g. children under 18 years of age.

At project start and each monthly follow-up

As with the participating residents, measures (listed below) will be repeated at monthly intervals. We shall inquire about contact with the ICL and whether end of life issues have been mentioned.

Zarit Burden Interview: a 22-item self-report questionnaire, the most consistently used measure of carer burden in dementia. The questionnaire asks the carer to reflect on how they feel when they are caring for the person (39). (See Appendix 12).

Hospital Anxiety and Depression Scale (HADS): a self-report instrument for clinically significant anxiety and depression (40). (See Appendix 13).

The Satisfaction with Care at the End of Life Scale in Dementia Scale (SWC/CAD-EOLD): a validated tool that quantifies overall satisfaction with care in advanced dementia. This brief 10-item self-administered questionnaire assesses the caregiver's level of satisfaction with decision-making, medical and nursing care, and their understanding of the condition of the person with dementia (See Appendix 14). The CAD version is used to assess care received around the time of death (36) (see data collection in bereavement - below). (See Appendix 11).

EQ-5D-5L: this instrument is an index-based utility set for the calculation of quality-adjusted life years (QALYs) used to inform health economic evaluations of healthcare interventions (41). (See Appendix 15).

Qualitative interviews

To gain a deeper understanding of how they experience the enhanced care model and working with the ICL we shall offer qualitative interviews with the research team and to all participating family carers in a place of their choice. These will occur at the end of the feasibility study for the enhanced model of care or in bereavement if the resident dies (for interview schedule see Appendices 16 and 17).

Data collection in bereavement

To gain a deeper understanding of the circumstances surrounding the death and the views of the carer on which aspects of care were or were not satisfactory, where possible we shall ask additional questions all bereaved family carers. In this case we will ensure these interviews take place two months after bereavement, this has been found to be the optimal time for such work whereby the carer feels ready to think about their loss but still has sufficient recall of events (42;43). We found in our cohort study that these interviews are acceptable (we have completed ten so far) and family carers are keen to reflect on their experiences (25). The SWC-EOLD scale will be completed to assess family carer's level of satisfaction with care

and the CAD-EOLD to assess the resident's level of comfort and pain in the 7 days prior to their death from the carer's perspective.

We will items from a topic guide similar to that used successfully in our cohort study which was acceptable to family carers (44). Interviews will be audio taped and transcribed verbatim (anonymised). They will last no longer than one hour and carers will be offered the opportunity to review transcripts to ensure accuracy.

Table 4: Summary of data collection

	Project start	During project (monthly for 6 months)	After death/ in bereavement	After project ends
Enhanced care team process data	x	x		
Care home level data	x	x		
Paid carers/ enhanced care team staff qualitative interviews				x
Residents				
Demographic information	x			
FAST scale	x			
Charlson Co-morbidity Index	x			
Medications	x	x		
Prior advance care plans and wishes documented	x			
Symptom burden/generalist clinical assessment	x	x		
Bedford Alzheimer Nursing Scale	x	x		
Pressure sore risk and severity	x	x		
Pain Assessment in Advanced Dementia	x	x		
Cohen Mansfield Agitation Inventory	x	x		
Neuropsychiatric inventory	x	x		
Symptom Management at the End of Life in Dementia Scale	x	x		
Quality of Life in Late dementia Scale	x	x		
Resource Utilization in Dementia Scale	x	x		
Burdensome interventions		x		
Sentinel events		x		
Comfort Assessment in Dying Scale			x	
Family carers				
Demographic data	x			
Zarit Burden Interview	x	x		

Hospital Anxiety and Depression Scale	x	x	x	
Satisfaction with Care at the End of Life in Dementia Scale	x	x	x	
Comfort Assessment in Dying Scale			x	
EQ-5D-5L	x	x	x	
Qualitative interviews			x	x

DATA ANALYSIS

Data will be collected at the start of the intervention, and at monthly time points until a resident dies or until the end of the intervention period (6 months). This will ensure a detailed understanding and, because of the mortality rates expected, minimize attrition. Data will be entered into a password protected anonymised database by the research team.

Quantitative analysis

We will use simple descriptive statistics to summarise process data and the outcomes collected by the ICL at the care home level (i.e. number of deaths in the last month etc.) We will describe the demographic and clinical characteristics of residents and family carers who participate in the data collection, as well as symptoms experienced, interventions received and any sentinel events. We will describe the symptom burden and quality of care received using SWEOLCD, QUALID. We will compare the scores to the results of our previous study in order to gain inferences on whether the enhanced care project makes a difference. The results will be summarised using mean and standard deviation or alternatives in case of non-normally distributed data. Appropriate plots will also be produced.

Qualitative analysis

The interviews will be audio-taped, transcribed verbatim and entered onto a qualitative software programme (Atlas-ti) for the coding, management and retrieval of data. Transcripts will be analysed and coded using Thematic Analysis. The data analysis process will follow the guidelines provided by Braun and Clarke (45) to develop meaningful themes and a rigorous approach to data analysis will be adopted by working to the quality framework recommended by Spencer (46). Throughout the analytic process, the researchers will engage in ongoing reflection with the use of memoing and reflective diaries to engage with the data further and refine emergent themes. Data triangulation will be achieved by interviewing both family carers and care home staff from a variety of work roles (i.e., care home manager, health care assistant, nurse) to explore the facilitators and barriers to the implementation of the enhanced model of care from different perspectives.

Final analyses

After full data collection ends, we will undertake definitive analyses to detail the demographic features of the cohort and assess the symptom management and their health care needs (using Stirling, Waterlow, NPI and sentinel events), taking into account repeated measures on individual subjects. We shall describe the level and nature of unmet needs and examine descriptively (using mean and standard deviations or suitable alternatives in case of non-normally distributed data and graphs) how comfort and quality of life change over time (using PAINAD, SM-EOLD, SW-EOLD and QUALID). We will describe the trajectory of carer wellbeing (HADS and Zarit Buden Interview) during their friend/relative's final stages of life with severe memory problems and how this may change if the resident dies, using plots of the of wellbeing over time.

Sample size

This is a pilot study and as such a formal power calculation is not appropriate. Numbers are chosen on pragmatic grounds as sufficient to demonstrate feasibility in terms of recruitment and acceptance of the intervention. We will aim to recruit 30 residents with severe memory problems from two care homes from which to collect individual outcome data.

Health economics

Health economic evaluation will consider resource allocation in caring for patients with severe problems and, where relevant, in their last 6 months of life, as well as the quality of life of their family carers and associated economic impact on these family carers in this period.

Data on resource and service use for people with severe memory problems (RUD-Lite) and economic burden on family carers (Zarit Burden Interview) will be collected both at baseline and monthly after the enhanced care project has been implemented. These data will be collated with unit costs data from *Unit Costs of Health and Social Care (2012)* (47;48) to obtain costs per patient from NHS (such as averted hospital admission, costs for a typical episode), costs from personal social services (such as training and education for care home staff) and costs from societal perspectives (such as local commissioners' decisions on scarce resource allocation, additional costs to public purse where caring responsibilities had been met by the state instead of family carers).

Economic evaluation of the quality-adjusted life years (QALYs) for family carers will utilize EQ-5D-5L instrument to assess if enhanced care project has resulted in greater utility attained for this group and associated cost-effectiveness.

PROJECT MANAGEMENT

Registration, sponsorship and indemnity

The project will be registered with the research departments at the participating CCG. University College London will be the project sponsor and provide insurance. The research team will obtain honorary clinical contracts for each participating CCG, adhering to the Marie Curie Palliative Care Research Unit's Lone Worker Policy (2012).

Data protection

Case Report Forms (CRF) for the study will be stored in accordance with the Declaration of Helsinki. Electronic data will be anonymised and stored on a password protected database. At the end of the study anonymised files will be stored securely in a secure UCL archiving facility.

Research network support

The programme has been adopted by the DeNDRoN (Dementias and Neurodegenerative Diseases Network)

Project Staffing

The person appointed to the ICL post will have extensive experience in the care of older people and their family carers in care home settings and with expertise in severe memory problems and social care. They will deliver the intervention with the core team. They will be supervised by the PI ([name]) and, given the nature of the work, offered supportive clinical supervision by [name]. The ICL will receive training to acclimatise them to the care homes in which they will be working and familiarise them with the intervention manual. They will have a monthly meeting with the project team to check adherence to the principles of the manual and to make any necessary adaptations to this. Two clinical researchers, from the Marie Curie Palliative Care Research Unit, who have extensive clinical and research experience with both palliative care and people with severe memory problems and family carers will collect the individual data for the evaluation of the enhanced care intervention. The researchers have particular skills in interviewing bereaved family carers and relatives.

Core study team

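### How carer scales are completed is neither fixed nor recorded, and the contact mode changes exactly between baseline and follow-up in an uncontrolled pilot

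*Protocol*

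**What the plan says.** Under Outcomes for family carers, the research team collects carer data in "face to face interviews at study entry within 14 days of the initial resident assessment and then every month, by post or over the telephone", according to the carer's preference. The next subsections name four scales: Zarit, HADS, SWC-EOLD and EQ-5D-5L. These "measures (listed below) will be repeated at monthly intervals", and Table 4 confirms project start and monthly for all four.

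The descriptions of the scales point to completion by the carer. Zarit is called a self-report questionnaire, HADS is "a self-report instrument for clinically significant anxiety and depression", and of the satisfaction scale the protocol says: "This brief 10-item self-administered questionnaire assesses". For EQ-5D-5L no form of completion is given.

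After a death, the protocol says of the bereavement interviews that "we will ensure these interviews take place two months after bereavement". SWC-EOLD is to be completed then, and Table 4 adds HADS and EQ-5D-5L. How the forms are completed at that point is not stated. Zarit is not scheduled after death.

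Three parts of the analysis read these scales over time:
- Final analyses, for distress and burden: "We will describe the trajectory of carer wellbeing (HADS and Zarit Buden Interview").
- Final analyses, for satisfaction, as part of "how comfort and quality of life change over time (using PAINAD, SM-EOLD, SW-EOLD and QUALID").
- Health economics, where EQ-5D-5L is used "to assess if enhanced care project has resulted in greater utility attained for this group".

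Nothing in the protocol holds a carer to one mode, records the mode, or takes it into account when change is read.

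**The concern.** Answers about burden, low mood and satisfaction with a relative's care can depend on whether a person is asking, and on whether that person is in the room. Here the kind of contact changes at one point: after the entry interview and before the first monthly value. Entry is also the start of the intervention, so the change in contact coincides with the before-to-during step.

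The study has two homes and no concurrent control group. A step at month 1 that comes from the way the questions were put would look like a step caused by the service. The EQ-5D-5L statement is the most exposed, because it attributes a gain in utility to the project. The trajectory plots are exposed through their first point. The pilot is also meant to inform a definitive trial, so an artefact at that step could carry forward into the choice of carer outcomes.

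**Working it through.** No figure in the plan needs reproducing, because the protocol gives no carer target, effect size or standard deviation. The check is what follows from each way of reading the entry interview.

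**Step 1. Does the mode change between entry and follow-up?**

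| How the scales are completed at entry | Carer then uses post | Carer then uses telephone |
|---|---|---|
| Interviewer asks the items | Changes: asked aloud, then private form | Changes in part: asked face to face, then asked by voice |
| Carer fills in the form | No change in who completes it | Changes: private form, then asked aloud |

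The only case with no change for anyone is self-completion at entry with every carer choosing post. The protocol secures neither condition. It speaks of data collected in interviews, it calls three of the scales self-report or self-administered, and it leaves the follow-up mode to preference.

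**Step 2. Which contrasts are touched?**
- Entry to any later month: touched for the groups marked as changing in Step 1.
- Months 1 to 6 among themselves: touched only if a carer switches between post and telephone. The preference rule allows this but does not say that it will happen.
- Before to after death: open for SWC-EOLD, HADS and EQ-5D-5L, because the mode in bereavement is not stated. Zarit has no value after death, so this contrast does not exist for burden.

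**Step 3. How many carers?** The protocol reports 26 carers for 61 residents in the earlier cohort and aims for 30 residents now. Assuming the same rate:

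26 / 61 × 30 = 12.8, about 13 carers.

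**Step 4. What could the shift amount to?** The spurious mean change equals the share of carers who cross modes times the mean shift among those who cross. Both are unknown. The share can be anything from 0 to 1. As an illustration only, take a shift anywhere from -0.3 to +0.3 SD among those who cross. The spurious mean change then also lies between -0.3 and +0.3 SD, and is zero if nobody crosses.

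For comparison, the standard error of a mean change in 13 carers, in SD units, is √(2(1 − r)/13), where r is the within-carer correlation. Assuming r between 0.5 and 0.7:
- r = 0.5: √(1.0/13) = 0.28
- r = 0.7: √(0.6/13) = 0.21

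Even the outer end of the illustration is therefore only about one to one and a half standard errors (0.3/0.28 = 1.1; 0.3/0.21 = 1.4). The data could not show such a shift clearly, and 13 carers are too few to adjust for it, least of all if the mode was not recorded.

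**The case against.** The strongest answer is that the entry sentence describes the contact and not how the forms are filled in. Three of the four scales are called self-report or self-administered, so carers may well complete them on paper at the visit. Those who then use post would stay on self-completion. This stands. A reader might infer that every carer changes mode, or that all carers shift in the same direction by some fixed amount. The documents support neither. Post and telephone differ in whether someone is asking, so a mixture of the two need not give a uniform shift, and the size and sign are not given anywhere. The answer does not close the point, though: telephone carers still cross modes under that reading, and the protocol does not state that the reading is the intended one.

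A reader might also infer a mode effect on burden from before to after a death. Table 4 rules this out, since Zarit is not collected then. For the other three scales an unstated mode is a gap, not a demonstrated switch.

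It is also fair to say that this is a descriptive pilot with no formal test, that change in carers is already uncontrolled for time and disease progression, that a choice of post or telephone helps retention, and that researchers independent of the service team collect the data, which lessens pressure to praise the service. These points limit the consequence. They do not justify leaving an avoidable source of change on the one step where an effect would be looked for.

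**Conclusion.** The point holds in limited form. The protocol changes the contact mode at the baseline-to-follow-up step and neither fixes nor records how the carer scales are completed. Depending on how the entry interview is run, the mode of completion changes for telephone carers only, or in some way for both groups. Without a control group, such a shift cannot be told apart from an effect of the service when change in satisfaction, HADS and Zarit trajectories or an EQ-5D-5L gain is read from entry.

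The size and direction are unknown from the documents. The figure of about 13 carers assumes the earlier cohort's rate; the SD range and the correlations are assumptions used only for scale. The consequence is for how change is interpreted, not for any test. This is a cheap improvement worth making before data collection.

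**What to change.** - State that carers complete Zarit, HADS, SWC-EOLD and EQ-5D-5L themselves on paper at the entry visit, with the researcher present only to explain.
- Keep each carer to one follow-up mode where possible: post by default, telephone for those who need it.
- Use paper self-completion of SWC-EOLD, HADS and EQ-5D-5L at any bereavement visit.
- Record the mode on every form.
- Mark the mode on the trajectory plots and show change from month 1 as well as from entry. Keep values that cross modes; with about 13 carers, discarding them would cost too much.

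Two limits remain. Telephone carers still move from paper to voice after entry, but this becomes visible. Month 1 already lies within the intervention, so change from month 1 misses any effect in the first weeks and supplements the entry value without replacing it.

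The cost is a few sentences in the protocol and one field on the form, with no extra contact. The downside is less month-to-month flexibility for carers and possibly a few more missing forms.
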